Central Hypothesis: FACBC PET/ultrasound fusion guided biopsy can detect more cancer per core than the standard 12-core TRUS-guided biopsy. The specific aims include:

Aim 1: To perform FACBC PET/CT directed, 3D ultrasound-guided biopsy and to determine if fusion targeted biopsy can detect more cancer per core than standard TRUS-guided biopsy.

We will recruit 36 patients who have suspicion of recurrent prostate cancer after definitive therapy such as radiotherapy or other non-prostatectomy focal therapy such as cryotherapy. Based on our clinical experience, at least half of the patients (N≈18) will have positive imaging findings in the prostate bed. These patients will undergo a standard 12-core systematic biopsy followed by PET/ultrasound fusion targeted biopsy at the same setting. Patients with negative scan will undergo the standard biopsy. We will determine (i) whether fusion targeted biopsy can detect more cancer per core than the standard biopsy; (ii) whether the addition of targeted biopsy to systematic biopsy increases the rate of diagnosis of Gleason 7 or greater cancer.

The patient will be in the same setting for the standard TRUS-guided biopsy and the PET/TRUS fusion targeted biopsy. The same setting allows us to directly compare the accuracy of the two biopsy approaches for the same patients. This sequential study is supported by the literatures. For example, the NIH team led by [name] is one of the pioneer groups in the field of MRI/TRUS fusion

targeted biopsy. In their study, "*Patients in the trial underwent a standard of care 12-core TRUS biopsy and MRI/US fusion guided biopsy in the same setting.*" (P.A. Pinto, P.H. Chung, A.R. Rastinehad, A.A. Baccala, Jr., J. Kruecker, C.J. Benjamin, S. Xu, P. Yan, S. Kadoury, C. Chua, J.K. Locklin, B. Turkbey, J.H. Shih, S.P. Gates, C. Buckner, G. Bratslavsky, W.M. Linehan, N.D. Glossop, P.L. Choyke, B.J. Wood, "Magnetic resonance imaging/ultrasound fusion guided prostate biopsy improves cancer detection following transrectal ultrasound biopsy and correlates with multiparametric magnetic resonance imaging," *The Journal of urology* 186, 1281-1285, 2011).

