4.6. Statistical Analysis

The PI consulted with [name] at the Winship Statistical ^{Co}re. The following description was provided by [name] for the analysis plan and sample size.

Analysis Plan: After we obtain the pathological results for each core from the standard TRUS-guided biopsy and the PET/TRUS fusion targeted biopsy, we will calculate the cancer detection rate per core. For example, we will calculate how many cores are able to detect prostate cancer in the standard TRUS-guided biopsy and how cores will detect cancers in the PET/TRUS-guided biopsy. Based on the total numbers of cores for each biopsy approach, we can calculate the cancer detection rate per core for each biopsy approach. In order to compare the detection rates between the PET positive and negative groups, Chi-square test will be used to compare the detection rates with standard biopsy between the two arms with FACBC scan positive and negative, respectively. Logistics will be further employed to test their adjusted effect after adjusting for other factors in the multivariate analysis. In the first specific aim, the goal is to determine if the PET/TRUS fusion targeted biopsy can detect more prostate cancer than the standard TRUS-guided biopsy. Therefore, among the FACBC positive arm, Kappa coefficient will be calculated to measure the correlation of the paired diagnostic results between the standard biopsy and the fusion targeted biopsy. McNemar's test will be further used to test on its significance.

Sample Size: We will recruit a total of 36 patients for this study. According to the inclusion criteria, approximately half of patients will have positive imaging scans and the other half negative. We determine the sample size in order to compare the performance of standard biopsy with the fusion targeted biopsy. We will expect to have 18 patients with FACBC positive, therefore, with McNemar's test, the sample size of 18 paired samples will achieve a power of at least 80% to detect a Kappa coefficient of 0.62 or higher between the two methods at the significant level of 0.05, assuming equal probability of positive or negative diagnosis outcome. We also like to determine the power to compare the detection rates of standard TRUS-guided biopsy between the PET positive and negative groups. With 18 FACBC positive patients and 18 FACBC negative patients, this study will have a power of at

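### For the per-man comparison of targeted with standard biopsy, section 4.6 answers a which-detects-more question with kappa, which is blind to direction, and names McNemar's test as the test of kappa, which it is not

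*Combined protocol and SAP*

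**What the plan says.** Section 3 words Aim 1 as "to determine if fusion targeted biopsy can detect more cancer per core than standard TRUS-guided biopsy". The Analysis Plan in section 4.6 restates it without a unit: "the goal is to determine if the PET/TRUS fusion targeted biopsy can detect more prostate cancer than the standard TRUS-guided biopsy". The next sentence draws its consequence from that goal: among FACBC-positive men, "Kappa coefficient will be calculated to measure the correlation of the paired diagnostic results between the standard biopsy and the fusion targeted biopsy". It is followed by "McNemar's test will be further used to test on its significance".

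The Sample Size paragraph repeats the pairing. It says that 18 pairs analysed with McNemar's test give at least 80% power to detect a kappa of 0.62 or higher at the 0.05 level, with positive and negative diagnoses equally likely. The 18 is an expected number: "We will expect to have 18 patients with FACBC positive".

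Two other analyses appear in the same section.
- Per-core rates: "we can calculate the cancer detection rate per core for each biopsy approach". No test or interval comparing the two approaches is stated.
- A PET-group comparison: "Chi-square test will be used to compare the detection rates with standard biopsy between the two arms with FACBC scan positive and negative", with a logistic model to adjust it. This compares PET-positive with PET-negative men on standard biopsy. It does not compare targeted with standard biopsy.

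Section 4.6 does not mention a paired difference in detection, a confidence interval, a report of the discordant counts, or a rule for direction.

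**The concern.** The question has a direction. Kappa has none: exchanging the labels of the two biopsies leaves it unchanged. It rises as the two methods agree, whereas a gain from targeting shows as disagreement in one direction. McNemar's test does bear on the question, because it tests whether the two detection rates are equal. The plan, however, presents it as the test of whether kappa is significant.

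A report that follows the text would give a kappa and a p-value that answer different questions. A small p-value could be read as significant agreement when it means that the methods differ. Close agreement would be labelled non-significant. Neither number says how many more men are detected by targeting, or how precisely. No other targeted-versus-standard inference is planned, so the confirmatory reading of this comparison rests on the kappa/McNemar pair.

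**Working it through.** **Inputs.** Section 4.6 gives 18 pairs, kappa 0.62, alpha 0.05, 50% positive and power of at least 80%. It does not state whether testing is one- or two-sided; two-sided is assumed unless noted. The tables below are illustrations, not forecasts. Cells are a = both positive, b = targeted only, c = standard only, d = neither, with n = a + b + c + d.

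**Formulas.**
- Observed agreement po = (a + d)/n.
- Chance agreement pe = [(a + b)(a + c) + (c + d)(b + d)]/n².
- Kappa = (po - pe)/(1 - pe).
- Difference, targeted minus standard = (b - c)/n.
- McNemar's test uses b and c only: exact p = 2 × P(X ≤ min(b, c)) with X ~ Bin(b + c, 0.5), capped at 1; asymptotic chi-square = (b - c)²/(b + c).

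**1. The plan's own figure.** Treat it as a test of kappa = 0 with both margins at 50%. The null SE is 1/√18 and the alternative SE is √(1 - 0.62²)/√18. Power = Φ[(0.62 - 1.96/√18)/(√(1 - 0.62²)/√18)] = 80.4%. The stated power therefore reproduces, but as power for agreement.

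The same scenario under McNemar's test: agreement is (1 + 0.62)/2 = 81%, so 19% of men are discordant, 9.5% each way. The two detection rates are equal and McNemar's null hypothesis is true. Its rejection rate with 18 pairs is 0.3% (exact) or 3.8% (uncorrected asymptotic), not 80%.

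**2. Kappa ignores direction.** For 6/6/0/6, po = 12/18 = 0.667 and pe = (12×6 + 6×12)/324 = 0.444, so kappa = 0.222/0.556 = 0.40. Exact p = 2 × 0.5⁶ = 0.031. Exchanging b and c changes neither statistic.

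| a/b/c/d | Targeted | Standard | Difference | Kappa | Exact p |
|---|---|---|---|---|---|
| 6/6/0/6 | 67% | 33% | +33 points | 0.40 | 0.031 |
| 6/0/6/6 | 33% | 67% | -33 points | 0.40 | 0.031 |
| 7/2/2/7 | 50% | 50% | 0 | 0.56 | 1.0 |
| 4/8/0/6 | 67% | 22% | +44 points | 0.25 | 0.008 |
| 9/0/0/9 | 50% | 50% | 0 | 1.00 | 1.0 |

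The last three rows show that McNemar's p-value does not test kappa: here the larger kappas carry the larger p-values.

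**3. Which kappas can be McNemar-significant?** All 18-pair tables with kappa defined (1,328) were enumerated. The largest kappa with two-sided p < 0.05 is:
- exact: 0.40, at 6/6/0/6;
- uncorrected asymptotic: 0.576, at 7/4/0/7, where po = 14/18, pe = (11×7 + 7×11)/324 = 0.475 and chi-square = 4²/4 = 4.0.

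Both lie below 0.62. If testing were one-sided in favour of targeting, the exact limit would be 0.48 (6/5/0/7, p = 0.5⁵ = 0.031). The uncorrected one-sided test would reach 0.67 (7/3/0/8: po = 15/18, pe = (10×7 + 8×11)/324 = 0.488, z = 3/√3 = 1.73). The statement that 0.62 can never be significant therefore holds for two-sided testing and for the exact one-sided test, but not for an uncorrected one-sided test.

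**4. What a paired difference would show.** For 6/6/0/6, the Agresti-Min interval adds 0.5 to each cell, so n = 20, b = 6.5 and c = 0.5. The centre is 6/20 = 0.30 and the SE is √(7 - 6²/20)/20 = 0.114. The 95% CI is 0.08 to 0.52. For 6/0/6/6 it is -0.52 to -0.08. The tables that kappa and p could not separate are now distinguished.

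**5. What 18 pairs can detect on this scale.** The table gives 80% power by two-sided exact McNemar. The standard-only share is an assumption, because the documents give none.

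| Standard only (assumed) | Targeted only needed | Detectable difference |
|---|---|---|
| 0% | 40% | 40 points |
| 2% | 46% | 44 points |
| 5% | 55% | 50 points |
| 10% | 68% | 58 points |

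With the uncorrected asymptotic test the differences are about 29, 36, 44 and 52 points.

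**The case against.** A reader might infer that the plan yields no direction or size at all for targeted against standard biopsy. The documents do not support that. Section 4.6 calculates a per-core rate for each approach, and two rates give a crude direction and size on the scale that section 3 names for Aim 1. What is missing there is a comparison test, an interval and an allowance for cores clustered within men.

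A reader might also infer that Aim 1 asks how many more men are detected. Section 3 words it per core; only the restatement in section 4.6 leaves the unit open. The per-man paired result is one part of the answer to Aim 1, not its defined scale.

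The best defence of the text is that McNemar's test is the right test for paired detection and that the wording around it is merely loose. The Sample Size paragraph does describe its purpose as comparing the two biopsies, and the test cannot be computed without the discordant counts, which show direction. This stands in part: an alert analyst would recover the answer. But kappa is the natural antecedent in the analysis sentence, the power sentence makes the same link, and nothing commits the team to reporting those counts or using them to settle direction.

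It would go too far to predict that a win for standard biopsy would be reported as a win for targeting; the documents contain no such rule. The tables used here are constructed and show a property of kappa, not an expected distortion in this trial.

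**Conclusion.** The point holds for the paired per-man comparison in FACBC-positive men. The chosen measure cannot tell which biopsy detects more, and the named test is attached to a quantity that it does not test. With 18 pairs and two-sided testing, significance is impossible above kappa 0.40 (exact) or 0.58 (uncorrected asymptotic), so the plan's target of 0.62 would always be labelled non-significant. Since the per-core rates carry no planned targeted-versus-standard inference, the kappa/McNemar pair is the only inference planned for this comparison.

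The algebraic point about kappa does not depend on any assumption. The limits on kappa assume exactly 18 men with both biopsies and the two-sided 0.05 level. The change should be made, but it is a repair to one analysis; it does not show that Aim 1 cannot be answered.

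**What to change.** In section 4.6, for FACBC-positive men who had both biopsies:

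- Report the full 2x2 table, both per-man detection rates, and the paired difference (targeted only minus standard only)/n with a 95% CI for paired proportions, for example Tango or Newcombe.
- State that McNemar's test tests this difference, in which version (exact or asymptotic) and with how many sides.
- State that targeted biopsy is concluded to detect more per man only if the test is significant and targeted-only exceeds standard-only.
- Keep kappa, if wanted, as descriptive agreement with its own CI, and delete the statement that McNemar's test gives its significance.
- Present this as the per-man paired analysis beside the per-core rates, not in place of Aim 1's per-core scale.

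The analysis change costs some wording and a little code, with no new patients, data or procedures. It has one real downside: the kappa-based sample-size sentence would no longer describe the analysis. It must be restated in terms of discordant proportions, which means admitting that 18 pairs detect only about 40 to 58 points at 80% power by exact McNemar, for assumed standard-only shares of 0% to 10%.

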least 80% to detect a difference in detection rates of 41% or higher between the two groups at the significant level of 0.05.

5. Registration/Randomization

Patients will be registered and consented into the study by one of the research nurses on staff working in the clinical Urology or Radiology setting. There will be no randomization. Patients are referred to the study by an Emory physician and or Co-I via email or telephone. Patient is seen at next appointment or at FACBC PET scan visit. Patient is then consented, registered into ERMS and eligibility criteria completed.

6. Intervention

This is not a therapeutic study. Diagnosis only.

Standard transrectal ultrasound (TRUS) guided biopsy: An ultrasound probe about 2.5 cm in diameter is gently inserted into the rectum. This ultrasound probe allows visualization of the prostate on two-dimensional (2D) images and allows for the placement of a biopsy needle that collects samples of the prostate. Usually, a total of 12 biopsy specimens are usually collected. The procedure takes about 20 minutes. This TRUS-guided biopsy is considered as the standard method for prostate cancer diagnosis. However, this biopsy procedure randomly takes tissue specimens from the prostate. Because of sampling errors, this standard TRUS-guided biopsy may miss the tumor in the prostate. In this proposed study, we will use three-dimensional (3D) ultrasound imaging to guide the biopsy in order to improve the location of the biopsy needle and will also use PET imaging to direct the biopsy to a suspicious target. The 3D ultrasound guided biopsy procedure is outlined in the next paragraph.

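### Is the 80% power claim for the FACBC-positive versus FACBC-negative comparison unsound because no detection rates are given?

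*Combined protocol and SAP*

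**What the plan says.** The analysis plan in section 4.6 names the test: "Chi-square test will be used to compare the detection rates with standard biopsy between the two arms with FACBC scan positive and negative". The sample size paragraph first deals with the paired comparison of the two biopsy methods, which is what fixed the number of patients: "We determine the sample size in order to compare the performance of standard biopsy with the fusion targeted biopsy". That calculation carries a rate assumption, "assuming equal probability of positive or negative diagnosis outcome".

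The paragraph then turns to a second question: "We also like to determine the power to compare the detection rates of standard TRUS-guided biopsy between the PET positive and negative groups". Its answer starts "With 18 FACBC positive patients and 18 FACBC negative patients, this study will have a power of at" and ends "least 80% to detect a difference in detection rates of 41% or higher between the two groups at the significant level of 0.05". The equal group sizes come from the expectation that "approximately half of patients will have positive imaging scans and the other half negative". For this second comparison the text gives the difference, the group sizes and the significance level. It does not give either group's detection rate, whether the test is one- or two-sided, or the formula used.

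**The concern.** For two independent proportions, the difference alone does not fix the power, because the variance depends on where the two rates lie. A claim of at least 80% at 41 points or more, with no condition attached, reads as a guarantee for any pair of rates that far apart. For a two-sided chi-square test with 18 per group it is not one: power is lowest when the rates straddle 50%.

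If both detection rates turned out to be mid-range, a non-significant result could be read as coming from a test with 80% power when the true figure was in the seventies. The 50% assumption in the same paragraph belongs grammatically to the kappa calculation, so a reader cannot be sure that it was meant to carry over.

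**Working it through.** **Inputs, all from section 4.6:** 18 patients per group; difference d = 0.41; significance level 0.05; chi-square test, read as two-sided and without continuity correction. The patient is taken as the unit, because the group sizes are counts of patients. The two rates p1 and p2 are not given, so they are varied.

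**Formulas**, with q = 1 − p and p̄ the mean of the two rates:

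- Pooled: power = Φ{[d − 1.96·√(2p̄(1−p̄)/18)] / √((p1q1+p2q2)/18)}
- Unpooled: power = Φ{d/√((p1q1+p2q2)/18) − 1.96}
- Exact: sum the binomial probabilities of all 19 × 19 outcomes for which the uncorrected Pearson |z| is at least 1.96.

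**Reproducing the plan's figure.** Take one rate at 50%, so the other is 9% (91% gives the same answer). Then p̄ = 0.295.

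- Null standard error: √(2 × 0.295 × 0.705/18) = 0.1520
- Alternative standard error: √((0.25 + 0.0819)/18) = 0.1358
- Pooled: (0.41 − 1.96 × 0.1520)/0.1358 = 0.825, so power is 79.5%
- Unpooled: 0.41/0.1358 − 1.96 = 1.06, so power is 85.5%
- Exact: 81.2%

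Solving for 80% power with one rate at 50% gives a difference of 41.2 points pooled, 39.0 unpooled and 40.5 exact. The stated 41 agrees with the pooled and exact results to within about half a point.

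**Moving the rates, with the difference held at 41 points:**

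| Rates | Pooled | Unpooled | Exact |
|---|---|---|---|
| 50% vs 9% | 79.5% | 85.5% | 81.2% |
| 55% vs 14% | 75.7% | 81.8% | 77.9% |
| 60% vs 19% | 73.0% | 79.1% | 76.5% |
| 70.5% vs 29.5% | 70.8% | 76.9% | 75.8% |

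The last row is the minimum for all three methods. For the pooled formula there: (0.41 − 1.96 × 0.1667)/0.1520 = 0.548, so power is 70.8%. With rates centred on 50%, 80% power needs 45.2 points pooled, 42.3 unpooled and 43.1 exact.

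Two-sided power is below 80% when the lower rate lies between 0.085 and 0.505 (pooled), 0.104 and 0.486 (exact), or 0.172 and 0.418 (unpooled). How much of the range falls short therefore depends on the method.

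**Sidedness.** With 1.645 in place of 1.96, the pooled worst case is (0.41 − 1.645 × 0.1667)/0.1520 = 0.893, so power is 81.4%. One-sided, the claim holds at every pair of rates 41 points apart.

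**Choice of test.** By exact enumeration, Fisher's test gives 70.4% at 50% vs 9% and 63.5% at the worst case; a continuity-corrected chi-square gives 69.8% and 63.5%. The plan names neither. In the other direction, the uncorrected test has a true size of 6.5% when both rates are 50%, so the exact column is slightly generous.

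**The case for a change.** The strongest case for a change is that the claim is worded as an unconditional lower bound. Under the natural two-sided reading of a chi-square test, that bound fails in the middle of the range whichever of the three formulas is used. The documents give no expected detection rate by FACBC group, so mid-range rates cannot be ruled out. At least two sets of assumptions lead to 41 points: two-sided from a 50% rate, and one-sided at any rates. A reader cannot tell which was used, and one sentence would settle it.

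What stands is that the statement is incomplete and that 80% is not assured for every pair of rates under a two-sided test. What does not follow is that the calculation is wrong. The usual way to quote a detectable difference is from a reference rate, and the one rate assumption in the same paragraph, 50%, returns the printed number.

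The documents' only general indication of biopsy yield, in sections 1.2 and 2, is that 70–80% of biopsies are negative. In two equal groups 41 points apart, a mean yield of 20.5–30% would put the lower rate at 0–9.5%, where exact power exceeds 80%. That yield is not specific to suspected recurrence after treatment, so it is weak support, but it does not point to the worst case.

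**Conclusion.** This is a gap in reporting that a statistician can fill from the same paragraph; it is not an arithmetic error. The 41-point figure is reproduced under a two-sided, uncorrected chi-square test with 18 patients per group and one rate at 50%.

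If the rates are instead centred on 50%, power at 41 points is about 71–77% across the three formulas. The detectable difference then grows by about 1 point (unpooled, 42.3 − 41), 2 points (exact, 43.1 − 41) or 4 points (pooled, 45.2 − 41). One patient in a group of 18 is 5.6 points (1/18), so the discrepancy is smaller than a single patient's outcome.

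The comparison did not determine the sample size, and the plan has no rule that ties the interpretation of a null result to the stated power. Stating the rates, sidedness and formula would leave enrolment, the test and the result as they are. No change is needed.

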A significant shift from baseline which can be attributable to the radiotracer injection and not the patient's medical condition will be considered an unexpected AE. An event greater than 7 days post scan will not be considered an AE since 95% of ligand is eliminated by 7 days.

The National Cancer Institute's Common Terminology Criteria for Adverse Events (CTCAE) Version 4.03 (June 14, 2010) will be used as a guide address potential AEs subject to limitations above and medical and scientific judgment as to plausibility of such criteria in a diagnostic radiotracer study.

Adverse Event Reporting

Any patient death that may be due to the study procedure (i.e. severe radiotracer reaction), unanticipated problem, would be promptly reported to the Emory IRB office. Additionally any patient death not associated with the study procedure or serious unanticipated event(s) (i.e. radiotracer allergy) will be reported to the Emory IRB and FDA upon continuing review. Protocol deviation/non-compliance will be reported according to IRB Policies & Procedures. This radiotracer is studied under IND 72437 and monitoring will be performed per already agreed upon FDA guidance. Over 900 patients in multiple centers have been studied without attributable serious adverse events.

A serious adverse event is any medical occurrence which is fatal, is immediately life threatening, requires hospitalization (or prolongs an existing hospitalization), results in persistent significant disability or incapacity, is a congenital abnormality or a birth defect, or is considered medically significant by a physician.

Serious adverse events will be communicated by the PI to the Emory IRB and FDA using standard adverse event reporting forms. Yearly safety reporting will also be forwarded to the FDA. Blue Earth Diagnostics, Ltd, (BED). BED is involved in the development and commercialization of FACBC for diagnostic purposes and will supply the FACBC cassettes for FACBC production. BED will receive data on safety since they supply the FACBC cassettes.

The Investigator will report all Serious Adverse Events occurring in a subject on the day of or within 28 days following the Agent administration to Pharsafer® Associates Ltd ("Pharsafer") by telephone ([name]), FAX ([name]) or e mail ([contact]). Pharsafer is the clinical research organization (CRO) that functions as the safety oversight on behalf of BED. Events should be reported to Pharsafer within 24 hours of the investigator becoming aware of the events occurrence.

10. Safety Monitoring

This study is being performed under the auspices of FDA IND 72,437. Patients will be monitored by the technologists and study nurse before and after the studies for any adverse events/reactions.

They will be given contact phone numbers to call if they experience any problems (i.e. problems with the IV site, any allergic reaction symptoms). They will be followed routinely by their referring physician with clinical exams, and the PI will work with the co-investigators and referring physicians to ensure that the patients continue to follow up as scheduled.

The Data and Safety Monitoring Committee (DSMC) of the Winship Cancer Institute will also oversee the conduct of this study (every 6 months or annually – depending on the risk level of the protocol). This committee will review pertinent aspects of study conduct including patient safety, compliance with protocol, data collection and efficacy. The committee will review the charts of 10% of patients enrolled to the study and two of the first 5 patients entered to the study. The Committee reserves the right to conduct additional audits if necessary. The Principal Investigator (PI) or designee is responsible for notifying the DSMC about the accrual of patients when the first 5 have been entered to the study. The PI or designee will also notify the DSMC of study status within 2 months before the next scheduled review is due.

Reference

Andriole,GL; Bullock,TL; Belani,JS; Traxel,E; Yan,Y; Bostwick,DG; and Humphrey,PA. Is there a better way to biopsy the prostate? Prospects for a novel transrectal systematic biopsy approach. *Urology*. 70:22-26. 2007.

Bao,P; Warmath,J; Galloway,R, Jr.; and Herline,A. Ultrasound-to-computer-tomography registration for image-guided laparoscopic liver surgery. *Surg.Endosc.* 19:424-429. 2005.

